1.4.2.2 Phase 1 Study in Patients with Cancer

Study I-196111 was a Phase I multi-center, dose-ranging study designed to determine the safety and tolerability of entolimod in patients with advanced cancers [20,21]. Entolimod doses of 5 (N=4), 10 (N=3), 15 (N=3), 20 (N=4), 30 (N=12), and 40 (N=7) μ g were evaluated with IM

injections given once daily for 5 days (Days 1-5) on a dose-per-subject basis through the 20 µg dose level and with IM injections once per day on Days 1, 4, 8, and 11 at the 30 µg and 40 µg dose levels.

Subjects ranged in age from 27 to 82 years and were primarily male and Caucasian. Body weights ranged from 40.7 kg to 117.3 kg. Subjects had a variety of cancer types; colorectal cancer and lung cancer were most commonly represented.

The safety results of Study I-196111 confirm that the commonly occurring AEs following entolimod administration are reflective of a “flu-like” syndrome, including chills, pyrexia, nausea, and vomiting. Expected transient treatment-emergent increases in leukocytes and neutrophils and decreases in lymphocytes and platelets, as well as treatment-emergent increases in serum ALT and AST levels, increases in serum glucose, and decreases in serum phosphate were observed. Expected transient, generally asymptomatic hypotension and tachycardia were also observed after entolimod injection; blood pressure recovered to pretreatment values with rest and fluids. When increases in QTcB occurred, they were almost universally low grade and did not show dose dependency; collectively, the ECG data do not suggest that entolimod causes clinically relevant disturbances of cardiac rhythm or conduction. Overall, the safety profile of entolimod in subjects with advanced cancers was found to be consistent with that observed in healthy subjects.

in serum glucose, and a decrease in serum phosphate. Predicted findings of transient, generally asymptomatic hypotension and tachycardia were also observed after entolimod injection; blood pressure recovered to pretreatment values with rest and fluids. Predicted increases in plasma cytokines (G-CSF, IL-6, IL-8, IL-10) and increases in circulating neutrophils and decreases in circulating lymphocytes (including B cells, T-cell subsets, and NK cells) were observed in the entolimod-treated subjects. Overall, the safety and pharmacodynamic profiles of entolimod in subjects with colorectal cancer in this study were consistent with those observed in healthy subjects and in previous studies in subjects with advanced cancer.

1.4.2.4 Entolimod in Combination with Vaccine

The Kadvax Technology study was performed to evaluate the safety and efficacy of 1 µg of entolimod receiving a commercial tetanus-diphtheria (Td) vaccine in healthy human subjects. The study enrolled 40 male volunteers (16 Caucasian, 24 non-Caucasian) between the ages of 18 and 40 years old (mean age = 28 years). Fifteen volunteers were enrolled in the control group and given commercial Td vaccine alone while 25 volunteers received the Td vaccine in combination with 1 µg of entolimod. Tetanus- and diphtheria-specific antibody titers were to determine if the addition of entolimod increased the vaccine response.

Mean baseline levels of tetanus toxoid (TT) -specific antibodies were relatively high in this study (2.95 IU/mL), and as a result, no subjects in the control (Td alone) or test (Td+entolimod) group had TT antibody responses above 6 IU/mL. Therefore, only subjects with pre-treatment-antibody titers below 3 IU/mL were included for data analysis (9 Td alone and 11 Td+entolimod). Eighty-two percent of the subjects that received entolimod with the Td vaccine showed a 2-fold or higher increase in their TT antibody titers, while only 33% of the control group showed this level of increase (chi sq = 4.3; p = <0.03). Two of the entolimod test subjects showed particularly strong increases in antibody titers (10- and 15-fold above baseline). A negative correlation was observed between baseline antibody titer and the change in antibody titer over 6 weeks. The correlation between lower baseline titer and greater post-vaccination change in titer was stronger in the Td+entolimod group than in the control group ($r = -0.73$ vs. -0.36). The negative correlation was statistically significant in the Td+entolimod test group with a p-value of <0.003. Analysis of anti-diphtheria antibody titers showed a greater increase in anti-diphtheria antibody titers for all 25 Td+entolimod test subjects versus the 15 Td alone control subjects (averaging 1.1 IU/mL vs. 0.9 IU/mL, respectively; p = <0.02). The negative correlation between baseline antibody titer and the change in anti-diphtheria antibody titer was also significantly stronger for the Td+entolimod group than for the control group ($r = -0.91$ vs -0.52 , respectively).

During this 6-week clinical trial, there were no treatment-related adverse events reported. Thus, IM injection of 1 µg of entolimod together with Td vaccine was found to be safe and to significantly increase the Td vaccine response.

1.4.2.5 Entolimod Safety in Elderly Subjects (≥ 65 years old)

Entolimod-specific treatment emergent adverse event (TEAE) data for 25 geriatric (≥ 65 years old) subjects was extracted from the studies performed in patients with advanced solid tumors (Study I-196111; 14 geriatric subjects) and in patients with colorectal cancer prior to primary tumor resection (Study BL612-CBLB502; 11 geriatric subjects).

The geriatric subjects ranged in age from 65 to 84 years, with thirteen subjects between 65 and 70 years, nine subjects between 71 and 80 years and three subjects between 81 and 84 years. There were 8 females and 17 males with screening body weights ranging from 47.2 kg to 107 kg. Sixteen (64%) of these subjects had colorectal cancer, while lung cancer (n=4), melanoma (n=2), anal cancer (n=2) and urothelial cancer (n=1) were also represented. For analysis, subjects were stratified into 3 groups based on the administered entolimod dose per kg of body weight: (i) <0.25 mg/kg, (ii) 0.25 mg/kg to 0.40 mg/kg, and (iii) >0.40 mg/kg with mean body weights of 77.7 kg, 79.1 kg, and 70.8 kg, respectively.

All subjects experienced a TEAE, but there was little evidence of a dose response when considering the total frequencies of any given type of event. Altogether, 175 TEAEs were reported among the 25 (100%) geriatric subjects. There did not appear to be a dose trend within any of the system organ classes (SOC) including general disorders, administrative site conditions, and respiratory, thoracic and mediastinal disorders. A majority (147) of the TEAEs were mild (Grade 1) or moderate (Grade 2) in intensity. Grade 3 TEAEs were largely laboratory abnormalities, except for single instances of cardiovascular events, including hypotension, hypertension and extrasystoles. The frequency of TEAEs of Grade ≥ 3 was nonexistent in the group receiving <0.25 mg/kg entolimod (<19.4 mg based on 77.7kg group mean body weight) but more prevalent in the group receiving >0.25mg/kg of entolimod (56%). Only 3/25 (12%) subjects ≥ 65 years experienced a Grade 4 AE (1 subject with hypophosphatemia, 1 subject with increased lipase, and 1 subject with both lymphocytopenia and neutrophilia). These subjects received a substantially higher entolimod dose (between 0.35 mg/kg and 0.45 mg/kg) than what is proposed for the current study.

No deaths occurred within this age group. Overall, within the limits of confidence imposed by the available number of geriatric subjects, there appear to be no differences in the safety profiles of people ≥ 65 years of age versus younger adult study subjects.

1.4.2.6 Entolimod and Subjects with TLR5 Mutation

A mutation has been identified in the TLR5 gene in which a cytosine-to-thymidine transition at base pair 1174 changes an arginine at amino acid 392 to a stop codon (TLR5_{392stop}) [22,23]. The TLR5₃₉₂ stop mutation is reported to occur in approximately 10% of humans in a heterozygous form and in 0.5% of the population in a homozygous form. The completed entolimod clinical trials described above included six subjects with TLR5₃₉₂ stop mutations: 1 subject who was homozygous for the mutation and 5 subjects who were heterozygous for the mutation. The 1 homozygous subject and 1 of the heterozygous subjects had almost no pharmacodynamic responses to entolimod. Of the remaining 4 heterozygous subjects, two had moderate responses and two had wild-type responses. Due to the small number of subjects with TLR5 mutations, it is not possible to draw definitive conclusions, but the data suggest that it will not be useful to screen patients for the presence of mutations in TLR5 prior to administration of entolimod. However, retrospective analysis of TLR5 functional status will prove useful for analysis in being able to definitively exclude non-responsive mutated TLR5 individuals.

1.5 Dose Rationale

Based on pre-clinical and clinical studies described above (sections 1.3 and 1.4), we hypothesize that a single IM injection of entolimod may significantly increase levels of anti-influenza antibodies, promote increased immunity, and delay or alleviate aspects of frailty. Risk is reduced by using single doses 5- to 50-fold less than those which are likely to cause adverse events, such as hypotension. The route of administration provides local delivery to the site of vaccination where the initial immune response to influenza antigens will occur.

1.6 Risks and Benefits

Entolimod used at doses similar to those to be used in this study has not previously been associated with adverse reactions. Based on the known safety profile of entolimod used at doses 5 to 50 times those proposed in this study, the following potential risks may be associated with the investigational drug: (1) flu-like symptoms, (2) decreases in blood pressure, (3) increases in heart rate, (4) hepatic transaminase elevations, (5) hyperglycemia, and (6) hypophosphatemia. All potential risks, if realized, are expected to be transient. Since entolimod will be given only once, the likelihood of long-term consequences is expected to be very low. Potential benefits include: (1) increasing influenza vaccine efficacy in an older population prone to poor vaccine responses, and (2) knowledge that might reasonably be expected from the study results (e.g., predicting early vaccine responses, better understanding of immunosenescence, and associations of vaccine responses with frailty). Therefore, the risks of using this drug are likely minimal compared to the anticipated benefits and the knowledge that may be gained from these clinical investigations.

1.6.1 Definition of DLT

Reference should be made to the Guidance for Industry Toxicity Grading Scale for Healthy Adult and Adolescent Volunteers Enrolled in Preventive Vaccine Clinical Trials for grading the severity of AEs and laboratory abnormalities where applicable. Based on the known safety profile of entolimod, flu-like symptoms are expected. Decreases in blood pressure, increases in heart rate, hepatic transaminase elevations, hyperglycemia, and hypophosphatemia are expected. DLT will be defined based on the sound clinical judgement of the investigator. DLTs will be considered adverse events and their time and grade severity will be recorded.

These risks and benefits are outlined in the Informed Consent Form and listed in the Investigators Brochure.

2 Study Objectives

Primary Objective

- To evaluate the effect of increasing dose of entolimod on enhancement of the influenza vaccine immunogenicity in the geriatric population (≥ 65 years old).

- To characterize the safety profile of entolimod within the geriatric population (≥ 65 years old) vaccinated against influenza.

Secondary Objectives

- To evaluate the pharmacodynamic effects of entolimod on immunological status, markers of senescence, viscoelasticity of tissue at the injection site, frailty indices and quality of life (QoL).

Exploratory Objectives

- To determine levels of anti-COVID-19 serum-circulating antibodies in a population of confirmed COVID-19 cases
- To determine the rate of the following occurrence in patients that become COVID-19 positive: (i) disease progression requiring hospitalization; (ii) acute respiratory distress syndrome (ARDS); (iii) and 30-day mortality following study drug administration.

3 Study Design

This clinical trial is a randomized, double-blind, placebo-controlled, dose-escalated, single-administration study evaluating the immunogenicity, pharmacodynamics, and safety of entolimod within the geriatric population (≥ 65 years old) vaccinated against influenza. After providing a written informed consent, subjects will undergo screening medical history, physical examination, vital signs, laboratory, and electrocardiogram (ECG) assessments within 28 days prior to study drug administration and influenza vaccination (see figure 2 below).

[figure not shown]
Eligible subjects will be seen at the clinical trial research unit (CTR) to receive the influenza vaccination (Fluzone, high-dose split virion influenza virus vaccine, Sanofi Pasteur) and a single IM injection of the study drug (entolimod or placebo). For safety assessment, initially 8 patients were to be enrolled in arm 1 (1ug) and accrual temporarily halted until the DSMB had assessed early adverse events. Due to the late seasonal start only four patients were successfully accrued to the study by the end of the flu season. A safety report was generated and the DSMB endorsed proceeding with enrollment of arm 2 (3ug) and arm 1 will restart. After 8 subjects have been enrolled into arm 2, accrual for arm 2 will be temporarily halted until the DSMB has assessed early adverse events. A safety report will be generated and enrollment of arm 3 (10ug) will commence and arm 2 will restart. After 8 subjects have been enrolled into arm 3, accrual for arm 3 will be temporarily halted until the DSMB has assessed early adverse events. A safety report will be generated and enrollment of all three arms will continue until enrollment is complete.

Unblinded and subject-level adverse event data will be provided to the Data Safety Monitoring Board (DSMB). If there is any evidence that higher doses are associated with adverse events, those study arms may be dropped, and the remaining planned patients accrued and randomized to remaining dose levels (and placebo) in equal proportions.

Subjects will be evaluated at the CRTU on the day of study drug administration (Day 1), for ≥ 6 hours (2hrs, 4hrs and 6 hrs), thereafter day 2, weeks 1 and 4, and then on months 2, 6 and 12. Between month 2 and 6 and 6 and 12 AEs will be reported and occurrence of respiratory infections will be assessed via phone interviews. Assessments of adverse events (AEs), vital signs/oxygen saturation including orthostatic measurements, clinical chemistry and hematology parameters (i.e., complete blood count with differential), ECGs, plasma cytokines, leukocytes, anti- A/H1N1, anti-A/H3N2, and anti-B influenza serum circulating antibodies including cellular immune response outcomes will be performed to describe drug safety, pharmacodynamics, and immunogenicity.

Subjects will be screened using a questionnaire for potential viral infection of COVID-19 at Day 1 and monthly through the end of the study. Subjects will be asked to provide a nasal swab and serum sample at Day 1 and Month 12. If at any time the subject is evaluated for COVID-19, the study team will document the symptoms, test results and treatment until resolution.

Figure 2. Flowchart of Study Events

NOTE: Subjects will also be contacted every two weeks by phone for Adverse Event monitoring.
Day 7 Safety Assessment will be completed as a remote visit

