HCV	Hepatitis C Virus
HIV	Human Immunodeficiency Virus
IB	Investigator's Brochure
IgG	Immunoglobulin G
IM	Intramuscular
IND	Investigational New Drug Application
IRB	Institutional Review Board
kD	Kilodalton
NHP	Non-human primates
PCR	Polymerase Chain Reaction
PHI	Protected Health Information
PI	Principal Investigator
RNA	Ribonucleic acid
SAE	Serious Adverse Event/Serious Adverse Experience
SARS-CoV-2	Severe Acute Respiratory Syndrome Coronavirus 2
SAVE	Sub-hertz Analysis of ViscoElasticity
SOP	Standard Operating Procedure
t _{1/2}	Mean terminal elimination half-life
Td	Tetanus-diphtheria vaccine
TEAEs	Treatment-emergent adverse events

TLR5	toll-like receptor 5
TLRs	Toll-like receptors
Tmax	Time at which maximum plasma concentration is observed
TT	Tetanus toxoid
UPIRTSO	Unanticipated Problems Involving Risk to Subjects or Others
ULN	Upper Limit of Normal
URI	Upper respiratory infection

Study Summary

Title	A Randomized, Double-Blind, Placebo-Controlled, Single-Administration, Dose-Escalated Study of Entolimod on Immunosenescence in Healthy Geriatric Subjects Receiving Influenza Vaccination
Running Title	Entolimod (CBLB502)
Protocol Number	19-004847
Phase	Phase II
Methodology	Double-blind, randomized placebo-controlled 4-arm study (3 active doses and placebo)
Overall Study Duration	Approximately 1- 1 ½ years
Subject Participation Duration	12 months from study drug administration
Single or Multi-Site	Single-Site
Objectives	Primary efficacy objective is to measure changes of the anti- A/H1N1, anti-A/H3N2, and anti-B influenza virus strains serum circulating antibodies (as assessed using hemagglutination inhibition (HAI) assay) levels
Number of Subjects	100 Subjects
Diagnosis and Main Inclusion Criteria	Elderly (age \geq 65 years) men and women who are medically stable and eligible to receive Fluzone High-Dose and have not received the flu vaccine within the past 90 days
Study Product, Dose, Route, Regimen	
This study will involve a dose-escalated, single dose administration of Entolimod (CBLB502) or placebo. Subjects will be randomized to one of the 4 arms:
 
 • Dose Level 1: 1 μg • Dose Level 2: 3 μg • Dose Level 3: 10 μg • Placebo 
The route of administration will be intramuscular.

Duration of Administration	Single dose administration
Reference therapy	Placebo-controlled

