4.2 Exclusion Criteria

Study candidates who meet any of the following criteria within 28 days prior to entolimod administration will not be eligible for participation in this study:

1. Receipt of any other vaccines within the past 30 days prior to enrollment
2. Acute illness within the last 7 days without systemic signs and symptoms including fever > 99.5
3. History of hypersensitivity to the flu vaccine or its components (including gelatin, formaldehyde, octoxinol, thimerosal, and chicken protein).
4. History of Guillain Barré syndrome (GBS)
5. History of bleeding disorders
6. Medical contraindication to treatment with vaccine as indicated by a history of autoimmune disease, immune deficiency, or hypersensitivity to other vaccines.
7. Unstable major cardiovascular, renal, endocrine, immunological or hepatic disorder
8. Systolic blood pressure (SBP) < 110 mmHg or orthostatic hypotension [>20 mmHg fall in SBP or >10 mmHg fall in diastolic blood pressure (DBP) with standing] at the time of screening.
9. Evidence of an ongoing systemic bacterial, fungal, or viral infection (including upper respiratory tract infections) (within 14 days prior to entolimod administration). **Note:** *Subjects with localized fungal infections of skin or nails are eligible.*
10. Baseline vital signs with \geq Grade 2 abnormalities
11. Significant cardiovascular disease (e.g., myocardial infarction, arterial thromboembolism, cerebrovascular thromboembolism, venous thromboembolism) within 6 months prior to study drug administration; symptomatic dysrhythmias or unstable dysrhythmias requiring

medical therapy; angina requiring therapy; symptomatic peripheral vascular disease; New York Heart Association Class 3 or 4 congestive heart failure; or uncontrolled Grade ≥ 3 hypertension (diastolic blood pressure ≥ 100 mmHg or systolic blood pressure ≥ 160 mmHg) despite antihypertensive therapy.

- a. Significant screening ECG abnormalities, including unstable cardiac arrhythmia requiring medication, atrial fibrillation, 2nd-degree atrioventricular (AV) block type II, 3rd degree AV block, or Grade ≥ 2 bradycardia (within 14 days prior to entolimod administration).
- 12. Inadequate hepatic function (within 14 days prior to entolimod administration):
 - a. Serum alanine aminotransferase (ALT) $\geq 3 \times$ upper limit of normal (ULN) (Grade ≥ 1).
 - b. Serum aspartate aminotransferase (AST) $\geq 3 \times$ ULN (Grade ≥ 1)

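### Exploratory objective (iii) counts 30-day mortality from dosing among subjects who become COVID-19 positive at any time in 12 months, which biases that one rate toward zero

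*Combined protocol and SAP*

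**What the plan says.** The second exploratory objective in section 2 is introduced as "To determine the rate of the following occurrence in patients that become COVID-19 positive". Three occurrences follow: progression to hospitalisation, ARDS, and "30-day mortality following study drug administration". No time limit is set on when a subject may become positive.

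The Study Summary gives participation as "12 months from study drug administration". Section 3 (Study Design) sets COVID-19 surveillance over the same period: "Subjects will be screened using a questionnaire for potential viral infection of COVID-19 at Day 1 and monthly through the end of the study". It adds that "Subjects will be asked to provide a nasal swab and serum sample at Day 1 and Month 12", and that if a subject is evaluated for COVID-19 at any point, "the study team will document the symptoms, test results and treatment until resolution".

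Section 3.6 lists one COVID-19 endpoint, infection detected by PCR. Mortality is not listed there, and section 7 contains no COVID-19 analysis. Nowhere do the documents restart the 30-day count at infection or diagnosis.

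**The concern.** The rate is conditioned on an event, becoming positive, that can happen at any time in a year. Its outcome window closes 30 days after dosing. For most of the year the outcome is therefore settled as alive before the qualifying event occurs. A subject who tests positive in month 5 and dies a week later would count as a 30-day survivor.

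At stake is the meaning of the reported figure. Section 13 states an intention to publish the exploratory results. A mortality rate among COVID-19 cases that is held near zero by its own definition could be read as evidence of mild disease or of benefit.

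**Working it through.** The plan gives no expected rate, event count or power for this objective, so there is no figure to reproduce. The check compares the two time windows.

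**Inputs from the documents.** Mortality window: 30 days from dosing (section 2). Follow-up: 12 months, taken as T = 365 days (Study Summary; section 8.1 also gives 365 days). Sample size: 100 (section 7.1).

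**Assumptions, because the documents are silent.** The timing of infections, the lag L in days from positive test to death, the 12-month attack rate, and the case fatality.

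**Step 1: the logic, with no assumptions.** A subject first positive after day 30 has survived the window. That subject adds 1 to the denominator and must add 0 to the numerator. This holds at any infection rate or case fatality.

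**Step 2: constant infection hazard.** By day 30, 30/365 = 8.2% of infections have occurred. A death is observable if infection occurs by day 365 − L, and inside the window if infection occurs by day 30 − L. The share of observable deaths inside the window is (30 − L)/(365 − L).

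| Lag L | Inside | Outside |
|---|---|---|
| 7 | 23/358 = 6.4% | 93.6% |
| 14 | 16/351 = 4.6% | 95.4% |
| 21 | 9/344 = 2.6% | 97.4% |

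About 94-97% fall outside.

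**Step 3: front-loaded hazard.** Let the hazard be k times higher in the first D = 90 days. The share inside is k(30 − L)/(kD + 365 − L − D).

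| k | L = 0 | L = 14 | L = 21 |
|---|---|---|---|
| 3 | 90/545 = 16.5% | 48/531 = 9.0% | 27/524 = 5.2% |
| 10 | 300/1175 = 25.5% | 160/1161 = 13.8% | 90/1154 = 7.8% |

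At k = 10, about 75-92% fall outside.

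**Step 4: effect on the rate.** With case fatality c and constant hazard, the expected rate as written is c × (30 − L)/365. For an assumed c of 10% and L = 14, this is 10% × 16/365 = 0.44%.

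**Step 5: how many deaths are involved.** With 100 subjects, an assumed attack rate of 5-30% and case fatality of 2-10%, expected COVID-19 deaths over 12 months run from 100 × 0.05 × 0.02 = 0.1 to 100 × 0.30 × 0.10 = 3. At L = 14 and constant hazard, the number inside the window is 0.1 × 16/351 = 0.005 to 3 × 16/351 = 0.14.

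**Step 6: count from the positive result instead.** A subject first positive by day 335 has a full 30-day window within follow-up. Under constant hazard that is 335/365 = 91.8% of infections.

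Eligibility points the same way as Step 2: section 4.2 excludes subjects with "Evidence of an ongoing systemic bacterial, fungal, or viral infection" shortly before dosing, which makes a COVID-19 death in the first 30 days less likely.

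**The case against.** **The phrase may not mean what it literally says.** The list is loosely punctuated, and the closing words could qualify all three occurrences, meaning events after dosing, with the 30 days intended from diagnosis. This is possible, and the lead-in about subjects who become positive favours it. But nothing in the documents says so, and on that reading the origin of the 30 days is not stated at all. The wording needs correcting either way.

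**A reader might infer that the trial loses most COVID-19 deaths.** The documents do not support that. Death is a serious adverse event under section 8.1, events are collected from consent through study completion (section 6.15) with a 365-day follow-up period (section 8.1), and COVID-19 evaluations are documented until resolution. The deaths will be in the database. Only this rate, taken literally, leaves them out.

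**A reader might also infer that the whole COVID-19 objective fails.** It does not. Hospitalisation and ARDS carry no 30-day limit and can be reported as proportions of positive subjects. They do not need a start date in common with mortality, and the antibody objective is untouched. The objective asks for a rate and names no comparison between arms, so no treatment-effect estimate is at risk in the plan.

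**The estimate will be imprecise on either clock.** This stands. With 0.1 to 3 deaths expected under the assumed rates, moving the time origin makes the rate correctly defined, not informative.

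**Conclusion.** The point holds, within narrow limits. As written, item (iii) is biased toward zero by construction, and that conclusion needs no assumption beyond some subjects first becoming positive after day 30.

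The size does depend on assumptions. The 94-97% figure rests on evenly spread infections and a 7 to 21 day lag. If infections were heavily concentrated early, with a hazard ten times higher in the first 90 days and a lag of 0 to 21 days, about 75-92% would fall outside. So most deaths fall outside the window in every scenario tried, and nearly all of them do if incidence is roughly even.

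The consequence is confined to one descriptive exploratory rate that has no matching endpoint in section 3.6 and no analysis in section 7. No primary, secondary or safety conclusion is affected.

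**What to change.** In section 2, define item (iii) as all-cause death within 30 days after the first positive SARS-CoV-2 result obtained after dosing. List it in section 3.6 as a descriptive item, so that the objective has a matching endpoint. If 30-day mortality after study drug is also wanted, report it separately as a safety item over all dosed subjects.

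The cost is a sentence in each section. Test results and deaths are already collected. A case first positive in the last month needs vital status to day 30 after the result. Section 8.1 already requires serious events ongoing at study end to be followed to their outcome, so the extra work is a vital-status check for non-serious late cases only. Under constant hazard, cases first positive after day 335 are 30/365 = 8.2% of infections.
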